8.6.3 Summaries of Baseline Characteristics, Demographics, and Other Analyses

8.6.3.1 Demographic and Baseline Characteristics

The comparability of the treatment groups for each relevant characteristic will be assessed by the use of tables and/or graphs. No statistical hypothesis tests will be performed on these characteristics. The number and percentage of subjects screened, enrolled in Period 1, enrolled in Period 2, the primary reasons for screening failure, and the primary reason for discontinuation will be displayed. Demographic variables (e.g., age, gender, race), baseline characteristics, primary and secondary diagnoses, and prior and concomitant therapies will be summarized either by descriptive statistics or categorical tables.

8.6.3.2 Antibodies to Golimumab

Blood samples will be collected to examine the formation of antibodies to GLM at the visits specified in the flow chart. Antibody data will be summarized as follows:

- Antibody status (positive/negative) of subjects will be summarized by treatment group. Further details about defining the treatment groups and approach to summarizing the data are described in a supplemental SAP.
 - GLM QM (both before and after Re-treatment, if needed);
 - GLM Q2M (both before and after Re-treatment, if needed);
 - PBO (both before and after Re-treatment, if needed).

In general, incidences of broad category AEs and injection-site reactions will be summarized by antibody status and treatment group.

- The proportion of subjects who show clinical response following re-treatment with GLM for a “flare” will be summarized by antibody status. The proportion of subjects who do not “flare” after withdrawal of GLM, or after reduction to GLM Q2M dosing, will also be summarized by antibody status. Efficacy endpoints (for example, ASDAS, ASAS20 response, ASAS40 response, and BASDAI50 response), occurrence of “flare”, clinical response after re-treatment for a “flare”, and antibody status will be listed by time point for subjects with positive antibody status.

8.6.3.3 Pharmacokinetic Data

The approach to summarizing the PK data is described in a supplemental SAP.

8.7 Interim Analyses

No interim analyses are planned for this study.

8.8 Multiplicity

The Type-I error rate over the multiple treatment comparisons will be controlled by a sequential (step down) testing procedure. Testing of the primary hypotheses will begin with comparison of the GLM QM versus PBO. The GLM Q2M versus PBO comparison will be performed only if the primary efficacy GLM QM versus PBO analysis is statistically significant at two-sided $\alpha = 0.05$.

All other efficacy analyses will be considered supportive and/or exploratory.

8.9 Sample Size and Power Calculations

A total of approximately 300 subjects will be enrolled. Assuming the proportion of subjects who attain inactive disease in Period 1 at both Months 7 and 10 is about 38% (based on the GO-AHEAD study, P07642 [1]), 300 enrolled subjects would result in approximately 114 subjects eligible for Period 2 of the study. With 114 subjects randomized in a ratio of 1:1:1 into the PBO, GLM QM, and GLM Q2M arms, 38 subjects are expected in each treatment arm.

Based on an expected proportion who do not “flare” of 80% in the GLM QM arm (based on study P07642) and 30% in the PBO arm (based on studies of subjects with early axial spondyloarthritis [7]), the power to detect a difference between treatment withdrawal (PBO) vs. continued treatment with GLM QM in the proportion of subjects who do not “flare” exceeds 99%, given $\alpha=0.05$ (2-sided). (See the bold text in Table 6 below.) If the primary hypothesis is rejected for the GLM QM vs. PBO (treatment withdrawal) comparison, then tests of GLM Q2M vs. PBO will be conducted. It is not known if the proportion who do not “flare” for the GLM Q2M arm will be similar to that for the GLM QM arm; but with a sample size of 38 per arm, the study will have 88% power to detect differences of 75% vs. 40% in the proportions of subjects who do not “flare”, should the estimates of absence of “flare” differ from what has been observed in prior studies [7]. (See the bold italic text in [Table 7](#) provides estimates of power for several response scenarios.

Table 7 Power for the Primary Endpoint, Comparing Two Treatment Arms

Treatment withdrawal: Placebo arm	Continued golimumab: QM or Q2M arm	
Proportion who Do not “flare” (N=38)	Proportion who Do not “flare” (N=38)	Power†
20%	80%	99%
	75%	99%
	70%	99%
	65%	98%
	60%	96%
30%	80%	99%
	75%	98%
	70%	95%
	65%	87%
	60%	75%
40%	80%	96%
	75%	88%
	70%	75%
	65%	59%
	60%	41%
†Assumes $\alpha=0.05$ and 2-sided test QM=every month; Q2M=every 2 months		

8.10 Subgroup Analyses and Effect of Baseline Factors

To explore whether the treatment effect is consistent across various subgroups, the estimate of the treatment effect (with a nominal 95% CI) for the primary endpoint, the proportion of subjects without a “flare” during up to 12 months, will be estimated and plotted within each category of each subgroup. The following are examples of classification variables:

- CRP category (>6.0 mg/L *or* ≤ 6.0 mg/L)
- MRI category for SI joint sacroiliitis (positive *or* negative)
- Gender (male *or* female)
- Age (≤ 30 years *or* >30 years)

In addition, a Forest plot will be produced, which provides the point estimates and confidence intervals for the treatment effect across the categories of subgroups listed above.

The consistency of the treatment effect will be assessed descriptively via summary statistics by category for the classification variables listed above.

8.11 Compliance (Medication Adherence)

Drug accountability data for GLM will be collected during the study. Compliance (also termed “medication adherence”) rates will be summarized (N, mean, median, standard deviation, range [min and max]) by period and by treatment group and overall in Period 2. The compliance rate for a subject will be defined as the total number of doses taken divided by the total number of doses the subject was supposed to take during the treatment period.

The number of injections (administrations) will be summarized similarly as described above for the compliance rates. In addition, descriptive statistics (counts and percentages) will be provided for the number of injections administered by period and by treatment group and overall in Period 2.

8.12 Extent of Exposure

The Extent of Exposure to study treatment will be evaluated by summary statistics (N, mean, median, and standard deviation) for the “Number of Days on Therapy” by Period and treatment group. A summary of total GLM exposure across Periods 1 and 2 will also be provided.

Period-2 duration of exposure will be calculated as follows:

- GLM QM group = the number of days from the first dose of GLM at Month 10 to the last dose + 30 days;
- GLM Q2M group = the number of days from the first dose of GLM at Month 10 to the last dose of GLM + 30 days;
- Placebo (withdrawal) group = number of days from Month 10 to the first dose of GLM given as re-treatment for a “flare” or to study discontinuation for subjects who don’t undergo re-treatment with GLM.

Due to the long half-life of GLM, the above subject-time computations will ignore the missing doses. The total subject-time of exposure for a group will be the sum of the subject-time of exposure of all subjects in the group.

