If a “flare” occurs during Period 2, then subjects discontinue blinded therapy (placebo, golimumab QM, or golimumab Q2M) and begin re-treatment with open-label golimumab QM. There should be an interval of at least 10 days between the last dose of Period-2 double-blind therapy and the first dose of open-label golimumab after a “flare” is confirmed. Thereafter, it is expected that re-treatment with open-label golimumab continues monthly through the end of Period 2. A clinical response to re-treatment is defined as a BASDAI score improvement of ≥ 2 or $\geq 50\%$ improvement (measured relative to the mean of the 2 BASDAI scores that were collected at the 2 consecutive assessments that defined the “flare”) that occurs within 3 months of restarting open-label treatment. If a subject shows insufficient improvement after 3 months of restarting open-label treatment for a “flare”, the investigator may consider discontinuing this subject from the study (based on clinical judgment) and will ensure a safety follow-up telephone call 3 months after the last dose of trial medication. If the subject is determined to have experienced a first “flare” between Months 19 and 22, the subject then completes a course of re-treatment (i.e., 3 monthly open-label golimumab injections) and will have a safety follow-up telephone call 3 months after the last dose of open-label golimumab. Subjects who do not experience a “flare” during Period 2 are to complete the study at Month 22 and will have a safety follow-up telephone call 3 months after their last dose of blinded trial medication.

Approximately 300 subjects are expected to enter Period 1. Based on the response to golimumab observed in the recently completed GO-AHEAD trial (P07642) [1], approximately 114 subjects are expected to continue into Period 2, based on attaining inactive disease status (ASDAS < 1.3) at both Months 7 and 10 of open-label golimumab. If the number of subjects who attain inactive disease is fewer than expected, additional subjects may need to enter Period 1 in order to randomize approximately 114 subjects with inactive disease status in Period 2.

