5.2 Trial Treatment(s)

The treatments to be used in this trial are outlined below in [Table 1](#).

Table 1 Trial Treatment

Biologic	Dose/Potency	Dose Frequency	Route of Administration	Regimen (Treatment Period)	Use
Golimumab	Per approved label: 50 mg (or 100 mg)†	Every month (QM)	Subcutaneous (SC)	Open-label from Month 0 to Month 9 (Period 1); switch to open-label golimumab upon “flare” (Period 2)	Standard of Care
Golimumab (full-treatment regimen)	Per approved label: 50 mg (or 100 mg)†	Every month (QM)	Subcutaneous (SC)	Double-blind monthly injections of active golimumab for 12 months (or until “flare”)	Experimental
Golimumab (reduced-treatment regimen)	50 mg (or 100 mg)†	Every 2 months (Q2M)	Subcutaneous (SC)	Double-blind monthly injections of active golimumab, alternating with placebo for golimumab, for 12 months (or until “flare”)	Experimental
Matching placebo for golimumab		Every month (QM)	Subcutaneous (SC)	Double-blind monthly injections of placebo for golimumab for 12 months (or until “flare”)	Experimental
† For subjects with body weight more than 100 kg, increasing the dose of golimumab to 100 mg may be considered during the Open-label Period 1 (and would continue during Period 2, depending on the randomization schedule).					

The frequency of SC injections is monthly during the entire trial. After an initial dose has been given, administration then continues preferably on the same day of every month (consistent with approved labeling) with an allowed window of ± 5 days. As the trial progresses, the day of the month that is targeted for dosing can be re-set, if needed (see Section 7.1.1.10). Depending on the period of the trial (open-label Period 1 or double-blind Period 2) and on the randomization schedule for treatment withdrawal or continued treatment (during Period 2), an individual injection may contain active golimumab or a matching placebo.

The first dose of golimumab 50 mg SC is administered at the study center by site personnel on the day of enrollment at Visit 2 (considered “Month 0”). If allowed by local guidelines and after proper training in injection technique, subjects may self-inject if determined by their physician that it is appropriate and with medical follow-up as necessary. For subjects with a body weight of more than 100 kg, increasing the dose of golimumab to 100 mg SC may be considered; see Section 5.2.1.2.

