8.6.1 Statistical Methods for Efficacy Analyses

This section describes the statistical methods that address the primary and secondary objectives. Methods related to exploratory objectives and related to analyses of data during Period 1 will be described in the supplemental SAP.

Efficacy data for continuous and categorical endpoints from Period 1 and Period 2 will be summarized separately. In Period 2, efficacy data will be summarized for each treatment comparison (GLM QM vs. withdrawal [PBO] and GLM Q2M vs. withdrawal [PBO]). In case of re-treatment following a “flare”, efficacy data will also be summarized for the time before re-treatment vs. the time after re-treatment.

The primary efficacy endpoint, the proportion of subjects without a “flare” (comparing between the PBO and GLM QM arms and between the PBO and GLM Q2M arms) will be analyzed using the stratified Miettinen and Nurminen (M&N) method [5], with stratification based on CRP level (>6.0 mg/L *or* ≤ 6.0 mg/L) and weighting scheme based on sample-size weights.

In addition, a comparison of GLM QM vs. GLM Q2M will be conducted as an exploratory analysis.

The exact binomial method of Clopper and Pearson [6] will be used to calculate a 95% CI on the proportion of subjects re-treated with golimumab after a “flare” who show a clinical response.

Missing data for the primary endpoint will be handled as follows:

- Discontinuations: Subjects who enroll in Period 2 but discontinue prior to a “flare” will be counted as having a “flare”.
- Missing components: If partial data are missing for the components of ASDAS (BASDAI questions 2, 3, 6, PGD_N, and CRP), then a multiple imputation (MI) procedure will be used to calculate the ASDAS. Details of the MI procedure will be provided in the sSAP.

Missing data for the secondary endpoint of proportion of subjects with a clinical response to re-treatment with GLM for a “flare” will be handled as follows:

- Discontinuations: Subjects who “flare” in Period-2 but do not undergo re-treatment or discontinue prior to re-attainment of inactive disease will be counted in the group having “flare” without clinical response to re-treatment.
- Missing components data will be handled similarly as for the primary endpoint.

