Tier 1 analysis will be performed in Period 2 only if there are at least 4 events in one of the treatment arms, using the Miettinen and Nurminen method for between-treatment differences in the percentage of subjects with events. In the case of less than 4 events in each treatment arms, the Tier 1 events will be listed by subject, treatment and period. Other safety parameters will be considered Tier 2 or Tier 3. Tier 2 parameters will be assessed via point estimates with 95% confidence intervals provided; only point estimates are provided for Tier 3 safety parameters. Adverse experiences (specific terms as well as system organ class terms) that are not pre-specified as Tier-1 endpoints will be classified as belonging to "Tier 2" or "Tier 3", based on the number of events observed. Membership in Tier 2 requires that at least 4 subjects in any treatment group exhibit the event; all other adverse experiences and predefined limits of change will belong to Tier 3. For this protocol, broad clinical and laboratory AE categories (consisting of the percentage of subjects with: Any AE, a Drug-related AE, a Serious AE, an AE that is both Drug-related and Serious, and Discontinued due to an AE) will be considered Tier 2 endpoints. Using the exact binomial method of Clopper and Pearson (Period 1) and Miettinen and Nurminen (Period 2), 95% confidence intervals will be provided for the percentages of subjects with events.

The threshold of at least 4 events was chosen because the 95% confidence interval for the between-group difference in percent incidence will always include zero when treatment groups of equal size each have less than 4 events and thus would add little to the interpretation of potentially meaningful differences. Because many 95% confidence intervals may be provided without adjustment for multiplicity, the confidence intervals should be regarded as a helpful descriptive measure to be used in review, not a formal method for assessing the statistical significance of the between-group differences in adverse experiences and predefined limits of change.

Safety data from Period 1 and Period 2 will be summarized separately. Period-2 safety data will be summarized for each treatment group (GLM QM, GLM Q2M, and PBO); in the case of re-treatment, safety data will also be summarized for the time before re-treatment vs. the time after re-treatment.

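### Section 8.12 stops Period-2 exposure at the first open-label re-treatment dose for placebo only, so the Q2M exposure figure, read literally, includes open-label monthly dosing

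*Combined protocol and SAP*

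**What the plan says.** Section 8.12 summarises days on therapy by period and treatment group and gives a separate Period-2 rule for each arm.

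- **Q2M:** "the number of days from the first dose of GLM at Month 10 to the last dose of GLM + 30 days".
- **QM:** the same form, from the first golimumab dose at Month 10 to the last dose plus 30 days.
- **Placebo:** "number of days from Month 10 to the first dose of GLM given as re-treatment for a" flare, or to study discontinuation for subjects who are not re-treated.

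Missed doses are ignored, and the days are added up: "The total subject-time of exposure for a group will be the sum of the subject-time of exposure of all subjects in the group". A total golimumab exposure summary across Periods 1 and 2 is planned as well.

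Section 2.1 says that after a flare in Period 2 "subjects discontinue blinded therapy (placebo, golimumab QM, or golimumab Q2M) and begin re-treatment with open-label golimumab QM". Monthly re-treatment is expected to continue to the end of Period 2. A first flare between Months 19 and 22 leads to a course of three monthly open-label injections. Table 1 in section 5.2 gives the Q2M regimen as "Double-blind monthly injections of active golimumab, alternating with placebo for golimumab, for 12 months (or until" flare, and lists the open-label switch in a different row, also under Period 2.

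**The concern.** The three rules produce figures that will stand side by side in one table, but they do not measure the same thing. On placebo, every re-treated flare shortens the credited time. On Q2M, a re-treated flare barely changes it, because the clock runs on through the open-label monthly doses.

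The reduced regimen is one of the questions the trial asks. A reader of the study report would take the Q2M row as the amount of experience on dosing every two months. Part of it would be monthly dosing in the subjects for whom the reduced regimen had failed.

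**Working it through.** The plan states no exposure figure to reproduce, so the check applies the rules as written.

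**Whether other text closes the gap.** It might be that golimumab in the Q2M rule means blinded golimumab only. But the placebo rule in the same section uses the same abbreviation, GLM, for the re-treatment product. It might be that Period 2 means blinded dosing only. But Table 1 and section 5.2 place re-treatment inside Period 2, up to Month 22. Sections 8.6.1, 8.6.2 and 8.6.3.2 split efficacy, safety and antibody summaries before and after re-treatment; section 8.12 carries no such split. No other section sets an end date for Q2M exposure.

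**One subject.** First open-label dose at Month 16, monthly dosing to Month 22, with the 30-day add-on taken as one month:

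- Q2M credit as written: 22 − 10 + 1 = 13 months.
- Open-label part: 22 − 16 + 1 = 7 months.
- Placebo subject with the same dates: 16 − 10 = 6 months.

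In days, at 30.4 days a month, the Q2M subject is credited about 395 days, against 183 if stopped at the first open-label dose. A Q2M subject who never flares and is dosed to Month 22 also gets 395.

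**Whole arm.** Inputs:

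- 38 subjects per arm (section 8.9).
- Proportion flare-free S = 0.8 or 0.6. This is an assumption within the range of Table 7; section 8.9 says the Q2M proportion is not known.
- Every flare is re-treated, at flare time t in months after Month 10, with density f(t).
- Re-treatment runs to Month 22, or for three doses if t is 9 or more.
- A subject who never flares has the last active dose at Month 22 and is credited 13 months.

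Mean blinded months per subject: B = 13S + ∫ t f(t) dt, over 0 to 12.

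Mean open-label months per subject: O = ∫ (13 − t) f(t) dt over 0 to 9, plus 3 ∫ f(t) dt over 9 to 12.

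Open-label share = O / (O + B).

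With flares spread evenly, f = (1 − S)/12. Then ∫ t f dt = 6(1 − S), and O = (1 − S)(117 − 40.5 + 9)/12 = 7.125(1 − S). With a constant hazard, f(t) = h exp(−ht) and h = −ln(S)/12, integrated numerically.

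| S | Timing | B | O | Share | Subject-years, 38 × O/12 |
|---|---|---|---|---|---|
| 0.8 | even | 11.60 | 1.425 | 10.9% | 4.5 |
| 0.8 | constant hazard | 11.555 | 1.467 | 11.3% | 4.6 |
| 0.6 | even | 10.20 | 2.85 | 21.8% | 9.0 |
| 0.6 | constant hazard | 9.997 | 3.042 | 23.3% | 9.6 |

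**What lowers the share.** Not every counted flare is re-treated. The primary endpoint treats early leavers as flares ("Discontinuations: Subjects who enroll in Period 2 but discontinue prior to a" flare are so counted in section 8.6.1). After three months of insufficient improvement on re-treatment, "the investigator may consider discontinuing this subject from the study (based on clinical judgment"). As an example, suppose half of counted flares are discontinuations or are not re-treated, each credited t + 1 months, all blinded. Then O halves and B rises by 0.5(1 − S). With even timing the share is 0.7125/(0.7125 + 11.70) = 5.7% at S = 0.8 and 1.425/(1.425 + 10.40) = 12.1% at S = 0.6. The one-half is an assumption; the documents give no split.

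**The case against.** The strongest defence is that the asymmetry is deliberate. Section 8.12 may be counting time on golimumab in the two golimumab arms and time off it in the withdrawal arm. A placebo subject changes state at re-treatment; a QM or Q2M subject is still on golimumab. For QM this largely stands: the wording mixes blinded and open-label time, but the dosing frequency is the same. For Q2M it does not answer the point, because two frequencies are merged under one regimen's label. A total golimumab summary is already planned for the reader who wants all time on drug.

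A second defence is that the sponsor means the last blinded dose. Table 1 ends the Q2M regimen at flare, and section 8.6.2 says that "in the case of re-treatment, safety data will also be summarized for the time before re-treatment vs. the time after re-treatment". That makes the intention plausible. It does not set the end date in section 8.12, so the literal rule remains the one a programmer would follow.

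A reader might go further and infer that the safety comparison is distorted, or that exposure-adjusted event rates are needed. The documents do not support that. Section 8.6.2 compares percentages of subjects with events by arm, and no planned analysis divides by the subject-time of section 8.12.

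**Conclusion.** The point holds as a minor one. As written, the Q2M exposure figure overstates experience on the reduced regimen and is built on a different end rule from the placebo figure beside it. The single-subject contrast follows from the wording alone. The arm-level size, roughly 11% to 23% of Q2M subject-time, rests on an assumed 60% to 80% flare-free, on full re-treatment and on assumed flare timing; it falls if some counted flares are discontinuations, are not re-treated, or stop re-treatment early.

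The end rules also differ for subjects who are never re-treated: last dose plus 30 days on QM and Q2M, study discontinuation on placebo.

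It would be wrong to read this as a flaw in the primary analysis, the power or the capture of adverse events. None of them uses these exposure rules.

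**What to change.** In section 8.12:

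1. End double-blind exposure at the first open-label re-treatment dose in all three arms.
2. State one common end rule for subjects who are never re-treated.
3. Report re-treatment exposure in a separate row by randomised arm, including any doses after Month 22 for late flares.

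The cost is one wording change and one extra table row per arm. Dose dates are already collected through the injection log and the case report form (section 7.1.1.10). The change should be made in the protocol or the supplemental SAP before unblinding, so that the choice of end date is not made after the data are seen.

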7.1.4 Other Procedures

7.1.4.1 Withdrawal/Discontinuation

Subjects who discontinue/withdraw from treatment prior to completion of the treatment should be encouraged to continue to be followed for all remaining study visits.

When a subject discontinues/withdraws from participation in the trial, all applicable activities scheduled for the discontinuation visit should be performed at the time of discontinuation. Any adverse events which are present at the time of discontinuation/withdrawal should be followed in accordance with the safety requirements outlined in Section 7.2 - Assessing and Recording Adverse Events and subjects will have a safety follow-up telephone call 3 months after their last dose of trial medication.

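### Section 8.12 ends Period 2 days on therapy by a different rule in each arm, so never-re-treated subjects with the same course generally get different values, and placebo completers have no stated end date

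*Combined protocol and SAP*

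**What the plan says.** Section 8.12 summarises days on therapy by period and treatment group and adds the individual times into a total for each group. For Period 2 it gives three definitions:

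- QM: "GLM QM group = the number of days from the first dose of GLM at Month 10 to the last dose + 30 days".
- Q2M: "GLM Q2M group = the number of days from the first dose of GLM at Month 10 to the last dose of GLM + 30 days". The clock follows the last active dose, not the last injection.
- Placebo: "number of days from Month 10 to the first dose of GLM given as re-treatment for a" flare, "or to study discontinuation for subjects who" do not go on to re-treatment. There is no 30-day extension and no link to the last injection.

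The section adds that, because of golimumab's long half-life, "the above subject-time computations will ignore the missing doses". That explains why gaps in dosing are disregarded. It does not explain why the three clocks stop at different events.

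Sections 5.2 and 5.2.3 have every arm injected monthly under blind. Section 7.1.1.10 has injection dates logged and entered in the eCRF. Section 7.1.4.1 says that subjects who stop treatment early "should be encouraged to continue to be followed for all remaining study visits".

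**The concern.** The golimumab rules measure time on drug. For a placebo subject who is never re-treated, the rule measures time in the study. All three results carry the same label, sit in adjacent columns and are summed into group subject-time.

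Stopping injections and leaving the study are separate events in this trial, so the two kinds of clock drift apart. A placebo subject who stops injecting but stays in follow-up keeps accruing days on therapy; a golimumab subject with the same course does not. In the other direction, a placebo subject who leaves within 30 days of the last injection gets fewer days than a QM subject who does the same. The difference has no fixed sign, so a reader cannot correct for it by eye.

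There is also a gap in the definition. The placebo clock ends at study discontinuation, but section 2.1 has subjects without a flare completing the study at Month 22, which is not a discontinuation. At stake is whether the by-arm duration figures that accompany the Period 2 safety tables can be compared.

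**Working it through.** The plan states no exposure figure, so there is none to reproduce. The check applies the three rules literally to identical courses.

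**Inputs**

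- Stop rules: section 8.12.
- Period 2 runs from Visit 24 (Month 10) to Visit 48 (Month 22), with a safety call at Month 25: section 6.2.
- Trial medication is given at Visit 48 but not at a discontinuation visit: section 6.2, note c.
- Follow-up after stopping treatment: all remaining visits encouraged (7.1.4.1), or about 3 months after the last dose for some reasons (5.8).
- Planning values: 38 per arm and 30% of placebo subjects without a flare (8.9).

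**Assumptions**

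- One month is 365/12 = 30.42 days.
- Q2M active doses fall at Months 10, 12, 14 and so on, since 8.12 puts the first golimumab dose at Month 10.
- No flare and no re-treatment.

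**Formulas.** In months after Month 10, let L be the last injection, A the last active injection under Q2M, and D the exit from the study.

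- QM = 30.42 × L + 30
- Q2M = 30.42 × A + 30
- Placebo = 30.42 × D
- Placebo minus QM = 30.42 × (D − L) − 30

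| Course | L | A | D | QM | Q2M | Placebo |
|---|---|---|---|---|---|---|
| a. Completer dosed at Visit 48, clock to Month 22 | 12 | 12 | 12 | 395 | 395 | 365 |
| b. Same, placebo clock to the Month 25 call | 12 | 12 | 15 | 395 | 395 | 456 |
| c. Completer whose last injection was at Month 21 | 11 | 10 | 12 | 365 | 334 | 365 |
| d. Last injection Month 13, leaves at Month 13.5 | 3 | 2 | 3.5 | 121 | 91 | 106 |
| e. Last injection Month 13, leaves at Month 14 | 3 | 2 | 4 | 121 | 91 | 122 |
| f. Last injection Month 13, followed 3 more months | 3 | 2 | 6 | 121 | 91 | 182 |
| g. Last injection Month 12, stays to Month 22 | 2 | 2 | 12 | 91 | 91 | 365 |

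**Reading the table**

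- Placebo minus QM is −30 days in (a), about +61 in (b), −15 in (d), +61 in (f) and +274 in (g).
- QM and placebo agree when exit falls about 30 days after the last injection, as in (c) and (e).
- Q2M is about one month below QM whenever the last injection was placebo, as in (c) to (f).

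**Group totals**

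- Completers: 0.30 × 38 = 11.4, so about 11 placebo subjects are expected to have no flare. If all complete and are dosed at Visit 48, placebo subject-time is 11 × 30 = 330 days lower than the QM rule would give for the same courses. If the clock runs to the Month 25 call, it is 11 × 61 = 671 days higher.
- Early stoppers: the documents give no rate. If 1 to 4 of 38 placebo subjects stop early and are not re-treated (assumed), the excess over the QM rule is 61 to 244 days with 3 months of follow-up each. If every one of them followed course (g), it would be 274 to 1,096 days.

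**Under one common rule** (last blinded injection plus 30 days), course (a) gives 395 in every arm, course (f) 121 and course (g) 91.

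**The case against.** The strongest reply is that the difference is deliberate. The placebo arm is the treatment-withdrawal arm and its injections contain no drug, so time off golimumab until re-treatment or exit is a sensible quantity for this design. So is counting only active doses under Q2M. That stands as a reason to report those quantities. It does not justify giving them the same label as the QM measure and setting them side by side.

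Three stronger readings might be inferred, and the documents do not support them.

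- *That early stopping in the placebo arm goes unseen.* Section 8.11 summarises compliance and numbers of injections by treatment group in Period 2, and section 8.6.3.1 displays the primary reason for discontinuation. Section 8.11 opens by referring to golimumab accountability data, but its summaries cover each treatment group.
- *That the safety or efficacy comparisons are distorted.* Section 8.6.2 compares percentages of subjects with events, and the plan specifies no exposure-adjusted rate. The primary endpoint is a proportion, and time to first flare has its own start and censoring rules in 8.6.1.
- *That gaps of about 274 days are typical.* Course (g) needs a subject to stop at Month 12 and remain 10 more months. Section 7.1.4.1 only encourages staying. Section 5.8 sets about 3 months of follow-up after some reasons for stopping, which gives about 61 days, and allows continued monitoring after others.

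It is also fair that, on the planning assumption, most placebo subjects flare and so fall under the re-treatment clause, which this point leaves aside.

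**Conclusion.** The inconsistency is real, and its reach is small. For never-re-treated subjects, section 8.12 applies three end rules to one labelled measure, no other section aligns them, and the placebo rule has no end date for those who complete at Month 22.

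Completers dosed at Visit 48 differ by 30 days, or by about 61 the other way, depending on how the missing end date is read. Early stoppers differ by about 61 days with 3 months of follow-up and by up to about 274 at the extreme. QM and placebo can coincide, so values differ generally but not in every case.

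The day counts rest on 365/12-day months and on Q2M active doses falling in alternate months from Month 10. The group totals also rest on the planned 30% without a flare and on an assumed number of early stoppers, so they are illustrations and not estimates. The consequence is confined to the descriptive exposure table and group subject-time. A correction is desirable but not critical.

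**What to change.** For subjects never re-treated, define Period 2 days on therapy identically in all three arms: from the first blinded injection at Visit 24 to the last blinded injection, active or placebo, plus 30 days. Report time since golimumab withdrawal as a separately labelled summary for the placebo arm, ending at re-treatment, study discontinuation or completion at Month 22, whichever applies.

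The cost is wording only. Injection dates are already collected, and section 8.0 provides the supplemental SAP for changes made before unblinding. One small downside is that Q2M days would include a final placebo interval when the last injection was placebo. Active-drug exposure should therefore stay in the total golimumab exposure summary across both periods that 8.12 already plans. A common end at study discontinuation or completion would also equalise the arms, but it would measure time in the study and should be labelled as such. Neither option settles the rule for re-treated subjects.
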